10.5 Laboratory Measurements

The following laboratory parameters will be measured:

- RT-PCR in NP swab
- Hematology: red blood cells (RBC), white blood cells (WBC) absolute neutrophil count, hematocrit, hemoglobin, platelets; C-reactive protein, international normalized ratio (INR), prothrombin time (PT)/ partial thromboplastin time (PTT)
- Blood chemistry: blood urea nitrogen (BUN), creatinine, alanine transaminase (ALT) and aspartate aminotransferase (AST)
- G6PD
- Pregnancy test (serum at screening and urine or serum at Day 12)

10.6 Other Measurements

10.6.1 Demographics

Patient demographics (gender, race, ethnicity, and age) will be recorded. Height and weight will be recorded.

10.6.2 Medical History

Medical history will be recorded including comorbid conditions and COVID-19 disease history.

10.6.3 Physical Examination

A physical examination of the oral cavity, head, eyes, ears, nose, and throat, cardiovascular system, lungs, abdomen, extremities, skin, neuropsychiatric mental status and sensory/motor status, musculoskeletal system and general appearance. Abnormal findings will be recorded.

10.6.4 Vital Signs

Vital signs including blood pressure, heart rate, oral or skin temperature and breathing rate (respiratory rate), will be recorded at the screening and Day 12 clinic visit after sitting for a least 3 minutes. Temperature, respiratory rate taken over a one minute period and oxygen saturation will be recorded daily at by the patient at home in the eDiary. Patients will be provided an oral thermometer to check and record in the eDiary their daily temperature and a home pulse oximeter to record their daily oxygen saturation.

10.6.5 Hospitalizations

Hospitalization information will be recorded on a hospitalization form and included in the case book that captures the PIs assessment of the hospitalization including the reason for hospitalization, length of stay, and details of the hospital visit. Patients will be asked to provide hospital records. Patients will be followed up as described in [Section 10.4](#).

10.6.6 Prior and Concomitant Medications

Medications including indication, start/stop date, dose, frequency, and route taken by the patient 14 days before the start of screening and for the duration of the follow-up period will be recorded on a source document and transcribed into an eCRF.

11 STUDY MANAGEMENT AND ADMINISTRATION

11.1 Adherence to Protocol

The investigator should not deviate from the protocol. However, the investigator should take any measure necessary in deviation from or not defined by the protocol in order to protect patients from any immediate hazard to their health and safety. In this case, this action should be taken immediately, without prior notification of the regulatory authority, IRB/IEC, or sponsor.

After implementation of such measure, the investigator must notify the sponsor within 24 hours and follow any local regulatory requirements.

11.2 Monitoring

Monitoring visits will be conducted by 60° Pharmaceuticals or designee according to applicable regulations and guidelines for GCP. The Investigator will permit the 60° Pharmaceuticals and/or designated representative(s) to make regular site visits during the study. The frequency of monitoring visits will be agreed upon by 60° Pharmaceuticals and/or designee. At each visit, the Investigator and staff will be expected to cooperate with 60° Pharmaceuticals or designee for the review and verification of protocol compliance, AE reporting, eCRFs, source documents, clinical supplies and inventory records, and any additional records as may have been previously arranged between the Investigator and 60° Pharmaceuticals or designated representative(s).

The Investigator and/or other designated study personnel are expected to contact the monitor of 60° Pharmaceuticals or designee as needed regarding study concerns and/or questions.

A Medical Monitor has been appointed by the Sponsor for the study. The Medical Monitor will be available for making recommendations to the investigator and the sponsor on the severity of any SAEs, and the relatedness to the study interventions. The Medical Monitor will also be responsible for tracking and assessing trends in the AEs reported.

11.2.1 Definition of Source Documents

It is the responsibility of the Investigator to collect and record all study data on source documents. The Investigator must provide access to source data/documents for study-related monitoring, audits, IRB/IEC review and regulatory inspection.

All source documents must be accurate, clear, unambiguous, permanent, and capable of being audited. They should be made using some permanent form of recording (ink, typing, printing, optical disc). They should not be obscured by correction fluid or have temporary attachments (such as removable self-stick notes). Photocopies and/or printouts of eCRFs are not considered acceptable source documents.

Source documents are original records in which raw data are first recorded. These may include hospital/clinic/general practitioner records, charts, diaries, x rays, laboratory results, printouts, pharmacy records, care records, or other printouts, completed scales, quality of life questionnaires, or video, for example. Source documents should be kept in a secure, limited access area. In cases where a device or instrument is the data originator (e.g., eDiary application) and data are automatically transmitted to the eCRF, then the eCRF is considered a source document.

Source documents that are computer generated and stored electronically must be printed for review by the monitor. Once printed, these copies should be signed and dated by the investigator and become a permanent part of the patient's source documents. The investigator will facilitate the process for enabling the monitor to compare the content of the printout and the data stored in the computer to ensure all data are consistent. In some cases, electronic source documents will be monitored electronically by the sponsor or designee and will not be printed. The Investigator must ensure that the sponsor or designee has access to the electronic medical record for patients if such a system is used.

Electronic data records must be saved and stored as instructed by 60° Pharmaceuticals (or designee).

Patient-reported outcome (PRO) measures will be completed by each patient and will be collected electronically.

The data collection and database management system will be supplied by a vendor and will be compliant with regulations. All data collected including data collected from the ePRO diary will be uploaded to a central server database and will be sent electronically to 60° Pharmaceuticals (or designee).

11.2.2 Source Data Verification

Source data verification ensures accuracy and credibility of the data obtained. During monitoring visits, reported data are reviewed with regard to being accurate, complete, and verifiable from source documents (e.g., patient files, recordings from automated instruments, x ray films, laboratory notes). All data reported on the CRF should be supported by source documents.

11.3 Data Handling

It is the Investigator's responsibility to ensure that data are collected and reported according to the study protocol. The Investigator will ensure the accuracy, completeness, and timeliness of the data reported on the eCRF and in all required reports. Efforts should be made to complete the eCRFs as soon after the scheduled visit as possible, and to have all eCRFs completed within 3 days after the Follow-up Visit.

Additionally, laboratory data will be received by Clinical Data Management from the appropriate clinical laboratory in electronic format. These data files may be merged with the clinical database.

11.3.1 Case Report Forms

Electronic CRFs will be produced according to protocol requirements, and access/training will be provided to all active sites in order for the Research Staff to record the data obtained on each patient during the study.

eCRFs must be completed for each patient enrolled (randomized) in the study. Data from patients that were screened but were ineligible for the study will not be included in the eCRFs, except that a Screen failure eCRF will be created to report the reason(s) that the patient was not eligible.

The CRFs must be kept up-to-date so that they always reflect the latest observations of the patients enrolled in the study. All records should be kept in conformance to applicable national laws and regulations.

11.3.2 Database Entry and Reconciliation

Case Report forms/external electronic data will be entered/loaded into a validated electronic database using a clinical data management system (CDMS). Computerized data cleaning checks will be used in addition to manual review to check for discrepancies and to ensure consistency of the data. Case Report form data are entered into the clinical database using independent, double data entry, with the exception of comment fields, which are verified by a second person. The data are entered into the electronic CRFs once and are subsequently verified if the study is performed using electronic data capture.

An electronic audit trail system will be maintained within the CDMS to track all data changes in the database once the data have been saved initially into the system or electronically loaded. Regular backups of the electronic data will be performed.

11.3.3 Patient Screening and Enrollment Log/Patient Identification Code List

The patient's screening and enrollment will be recorded in the Patient Screening and Enrollment Log. The investigator will keep a Patient Identification Code list. This list remains with the investigator and is used for unambiguous identification of each patient.

The patient's consent and enrollment in the study must be recorded in the patient's medical record. These data should identify the study and document the dates of the patient's participation.

11.3.4 Quality Control and Quality Assurance

The following steps will be taken to ensure the accuracy, consistency, completeness, and reliability of the data:

- Routine site monitoring;
- CRF review against source documents;
- Data management quality control checks;
- Statistical quality control checks;
- Continuous data acquisition and cleaning; and
- Quality control of final report.

A representative from 60° Pharmaceuticals and /or authorized representatives may conduct periodic audits of the clinical sites and study processes, including, but not limited to, the clinical database and the final report. The study may also be patient to inspection by regulatory authorities. The Investigator hereby agrees to allow access to required patient records and other documentation and facilities related to the review and conduct of the study.

11.4 Study Termination

The study may be terminated at any time at the request of 60° Pharmaceuticals or the Investigator with proper and timely notification of all parties concerned. The IRB/IEC will be informed promptly and reasons for the termination or suspension will be provided by the Investigator, as specified by the applicable regulatory requirements. The study can be considered complete and/or terminated after 60° Pharmaceuticals has received the following data and materials:

- Laboratory findings, clinical data, and all special test results from screening through the end of the follow-up period
- CRFs properly completed (including all system or manually-generated edit checks properly answered and closed) by appropriate study personnel and signed by the Investigator
- Completed Drug Accountability Records
- Statement of outcome for each serious adverse event reported
- Approval/notification of protocols and protocol amendments from IRB/IEC as well as relevant health authorities (if applicable).

11.5 Archiving and Data Retention

An Investigator is required to maintain adequate records of the disposition of the drug, including dates, quantity, and use by patients. If the investigation is terminated, suspended, discontinued, or completed, the Investigator shall return the unused supplies of the drug to the sponsor, or otherwise provide for disposition of the unused supplies of the drug under the U.S. Code of Federal Regulations 21 part 312.59.

An Investigator shall retain records required to be maintained under this part for a period of two years following the date a marketing application is approved for the drug for the indication for which it is being investigated; or, if no application is to be filed or if the application is not approved for such indication, until two years after the investigation is discontinued and FDA is notified.

60° Pharmaceuticals should inform the Investigator(s)/institutions(s) in writing of the need for record retention and should notify the Investigator(s)/institutions(s) in writing when the study related records are no longer needed.

Custody of the records may be transferred to another responsible part, acceptable to 60° Pharmaceuticals, who agrees to abide by the retention policies. Written notice of transfer must be submitted to 60° Pharmaceuticals. The Investigator must contact, and obtain the prior written permission of, 60° Pharmaceuticals prior to disposing of or so transferring any study records.

11.6 Audit and Inspection

The investigator will permit study related audits mandated by 60° Pharmaceuticals, after reasonable notice, and inspections by domestic or foreign regulatory authorities. The main purposes of an audit or inspection are to confirm that the rights and well-being of the patients enrolled have been protected, that enrolled patients (i.e., signing consent and undergoing study procedures) are appropriate for the study, and that all data relevant for the evaluation of the study drug have been processed and reported in compliance with the planned arrangements, the protocol, investigational site, and IRB/IEC SOPs, ICH GCP, and applicable regulatory requirements.

The investigator will provide direct access to all study documents, source records, and source data. If an inspection by a regulatory authority is announced, the investigator will immediately inform 60° Pharmaceuticals (or designee).

11.7 Good Clinical Practice

This study will be conducted in compliance with the protocol, GCP as defined by the U.S. Code of Federal Regulations 21 parts 50, 56 and 312, Sponsor policies and procedures and all applicable state regulations.

Noncompliance with the protocol, ICH GCP, or local regulatory requirements by the investigator, institution, institution staff, or designees of the sponsor will lead to prompt action by 60° Pharmaceuticals to secure compliance. Continued noncompliance may result in the termination of the site's involvement in the study.

12 STATISTICAL METHODS

This section describes the planned statistical analyses in general terms. A complete description of the methodology will be specified in a statistical analysis plan (SAP), which will be finalized prior to database lock and unblinding. Any changes in the statistical methods described in this protocol that occur prior to database lock and unblinding will be documented in the statistical analysis plan and will not require a protocol amendment.

12.1 General Statistical Considerations

Statistical hypothesis testing will be performed at two sided alpha level of 0.05. For continuous variables, population size (N for sample size and n for available data), the mean, the standard deviation (SD), the median, the minimum and maximum values will be tabulated. For categorical variables, number and percentage in each category will be tabulated.

12.2 Analysis Populations for Analyses

Three patient populations will be defined:

- The modified Intention-to-Treat (mITT) population will include all patients who took at least one dose of study medication and had at least one post start of treatment assessment. The mITT population is analyzed as randomized, regardless of which treatment a patient received.
- Safety population: Any patient randomized and received any dose of study drug. Safety population is analyzed based on the actual treatment received.
- The PP population includes all mITT patients completing the Day 12 [± 1 day] in clinic visit without any major protocol deviations. Protocol deviation category (minor or major) will be determined prior to the database lock and unblinding.

Efficacy endpoints will be analyzed for the mITT population. Analyses of efficacy endpoints in the PP population will provide supportive evidence. Safety summaries will be based on the Safety population.

12.2.1 Patient Disposition

Study completion, number of patients in mITT, PP, Safety populations, and reasons for discontinuation for all randomized patients in the double-blind phase will be summarized for each treatment group by simple tabulation. Discontinuations by reason will be tabulated for each treatment group. The reasons that patients did not meet eligibility criteria (screen failures) will be provided in a listing.

12.2.2 Demography and Other Baseline Data

Demographic data will be tabulated by treatment group in the mITT population. Past and current medical history will be summarized by treatment group using the system organ class (SOC) as coded using the Medical Dictionary for Regulatory Activities (MedDRA) coding dictionary.

12.2.3 Study Medication

Exposure and compliance will be presented as summary statistics by treatment group.

12.2.4 Prior/Concomitant Therapy

Prior/concomitant therapy will be summarized.

Any medications or therapy present before the first dose of study medication will be considered as prior medications. Concomitant medications (medications present while on study medication) will be recorded throughout the study and at early discontinuation. These medications will be coded using the WHO-drug dictionary. The number and percentage of patients from the safety population using prior or concomitant medications will be categorized by the WHO-drug class 4 name and presented for each treatment group. In any given category (e.g., drug category) a participant will be counted only once.

12.3 Planned Efficacy Analyses

12.3.1 Analysis of the Primary Efficacy Variable

The proportion of patients with clinical recovery at Day 12 will be analyzed using two methods: a 2x2 contingency table and logistic regression. The contingency table will provide unadjusted estimates of the proportions of patients with clinical recovery at Day 12. Copper-Pearson exact 95% confidence intervals around the recovery proportion within each treatment group will be provided. If 95% or more patients on the TQ arm have clinically recovered, then no logistic regression will be performed due to too few events then a Fisher's exact test will be used to compare treatment groups. However, if the rate is less than that then a logistic regression will be utilized. Treatment group will be the primary independent factor in the logistic regression. Additional covariates will be included in the model for every 10 events observed (eg, if at least 20 events then clinical site will be included, at least 30 events dichotomized number of symptoms (1-2 vs 3-4). Selection of additional covariates will be based on their relationship to the primary endpoint and correlation with other covariates. Patients who do not have a Day 12 visit due to hospitalization for COVID-19 symptoms will be considered treatment failures.

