5.1.2 Secondary

- Proportion of patients with negative SARS-CoV-2 RT-PCR on Day 12
- Hospitalization rates due to COVID-19 symptoms (excluding admittance only for administrative or observations purposes)
- Number of COVID-19-related medical follow up visits (Doctor's office or ER visit)
- Proportion of patients with COVID-19 symptoms at Day 12 by individual symptom

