6.1.3 Randomization

Eligible patients will be randomized at 1:1 ratio to receive TQ or placebo and stratified by site. Randomization will be performed through a centralized, web-based, validated system that automates the assignment of patients to treatment assignment. The randomization scheme will be reviewed and approved by the sponsor or designee. For study medication dispensation, the Investigator or designee will access the randomization system to determine which blinded study medication bottle the patients will be assigned.

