7.2 Exclusion Criteria

Patients are not permitted to enroll in the study if any of the following criteria is met:

- (1) Have any of the contraindications for ARAKODA or KODATEF in the prescribing information ([Section 15.1](#)) including:
 - a. G6PD deficiency
 - b. Breastfeeding
 - c. Psychotic disorder or current psychotic symptoms
 - d. Known hypersensitivity reaction to TQ
- (2) Evidence of severe or critical illness, defined by at least one of the following:
 - a. Clinical signs indicative of severe systemic illness with COVID-19, such as respiratory rate ≥ 30 breaths per minute, heart rate ≥ 125 beats per minute, $\text{SpO}_2 \leq 93\%$ on room air
 - b. Respiratory failure defined based on resource utilization requiring at least one of the following:
 - i. Endotracheal intubation and mechanical ventilation, oxygen delivered by high flow nasal cannula (heated, humidified, oxygen delivered via reinforced nasal cannula at flow rates > 20 L/min with fraction of delivered oxygen ≥ 0.5),

noninvasive positive pressure ventilation, extracorporeal membrane oxygenation (ECMO), or clinical diagnosis of respiratory failure (i.e., clinical need for one of the preceding therapies, but preceding therapies not able to be administered in setting of resource limitation)

- ii. Shock (defined by systolic blood pressure < 90 mmHg, or diastolic blood pressure <60 mmHg or requiring vasopressors)
- iii. Multi-organ dysfunction/failure

(3) Any other clinically significant acute illness unrelated to COVID-19 within seven days prior to first study drug administration

(4) Receipt of any experimental treatment for COVID-19 (off-label, compassionate use, or study-related) within the 30 days prior to the time of the screening evaluation

(5) Any excluded concomitant medication as described in the ARAKODA package insert ([Section 15.1](#))

(6) Any COVID-19 symptoms which, in the opinion of the investigator, is suggestive of possible requirement to hospitalize within 48 hours of enrollment

(7) Positive pregnancy test

(8) Have been symptomatic for more than five days when the first dose would be administered

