12.3.2 Other Efficacy Analyses

Dichotomous secondary endpoints will be analyzed in the same manner as the primary endpoint. The number of medical follow-up visits tabulated to determine if the endpoint can be considered continuous or ordinal. If the data are continuous the treatment groups will be compared by t-test. If the frequency distribution indicates few numbers of visits (eg 0, 1, 2, and 3 visits) then the analysis will use a chi-squared test to compare treatment groups. The methods for the conduct of the exploratory efficacy analyses will be provided in the SAP. Other *ad hoc* analyses not specified in the SAP may also be performed to further explore the data to aid in the design of future studies.

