12.6 Determination of Sample Size

The sample size calculation is based on the primary endpoint of recovery rate.

In a study of nonhospitalized patients with COVID-19 disease reported by [Skipper \(2020\)](#), placebo treated patients had resolution of clinical symptoms of COVID-19 by Day 14 in 70% of patients. Assuming an 85% clinical recovery rate in the TQ group and a 70% clinical recovery rate in the placebo group, sample sizes of 125 per treatment group will achieve 80% power with a two-sided alpha of 0.05 by logistic regression analysis.

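### The switch of the primary test to Fisher's exact test is triggered by the TQ arm's recovery rate alone, so it does not measure sparse events and depends on which arm does well

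*Combined protocol and SAP*

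**What the plan says.** Section 12.3.1 plans a 2x2 table and a logistic regression for clinical recovery at Day 12. It sets one condition for leaving the regression: "If 95% or more patients on the TQ arm have clinically recovered, then no logistic regression will be performed due to too few events". Fisher's exact test is then used, with no stratification mentioned. Below 95% on TQ, logistic regression is used whatever the placebo result.

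The same paragraph counts events when choosing covariates: "Additional covariates will be included in the model for every 10 events observed", for example "if at least 20 events then clinical site will be included", with number of symptoms added at 30. Section 6.1.3 has patients "randomized at 1:1 ratio to receive TQ or placebo and stratified by site". Section 12.3.2 extends the method: "Dichotomous secondary endpoints will be analyzed in the same manner as the primary endpoint". Those endpoints include the hospitalisation rate in section 5.1.2. The synopsis mentions covariates subject to sufficient events, but not the 95% switch.

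**The concern.** Too few events is a property of the whole table. A rule that reads one arm can fire when events are plentiful and stay silent when they are scarce. It also treats two results that differ only in the arm labels differently, which a two-sided comparison of two arms should not do. At stake are the power of the primary test if recovery is high, a clear reason for the choice of test, and a usable rule for rare secondary outcomes such as hospitalisation.

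**Working it through.** **Inputs.** 125 per arm, 85% versus 70% recovery, 80% power, two-sided 0.05 (sections 12.6 and 12.1); the 95% trigger and the 20- and 30-event steps (12.3.1). An event is read as a non-recovery, the only reading under which high recovery means few events. One covariate at 20 events and two at 30 imply 10 for treatment alone.

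**The plan's own figure.** ln OR = ln(0.85/0.15) − ln(0.70/0.30) = 0.887. SE = √[1/(125×0.85×0.15) + 1/(125×0.70×0.30)] = 0.318. Power ≈ Φ(0.887/0.318 − 1.96) = 79.8%. Exact enumeration of the unadjusted Wald test gives 81.7%. The stated 80% is reproduced.

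**When the switch fires.** 118/125 = 94.4% and 119/125 = 95.2%, so it needs at least 119 recoveries on TQ. The binomial probability by true TQ rate is:

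| True TQ rate | 85% | 90% | 92% | 93% | 95% | 96% | 97% |
|---|---|---|---|---|---|---|---|
| P(switch) | 0.03% | 2.8% | 12% | 22% | 57% | 77% | 92% |

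**Events present when it fires** (both arms combined):

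| TQ / placebo | At least 10 events | At least 20 events |
|---|---|---|
| 95 / 85 | 99.98% | 81.5% |
| 96 / 88 | 99.5% | 45% |
| 97 / 90 | 96.5% | 16% |
| 99 / 93 | 55% | 0.2% |

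For a single table, TQ 119/125 versus placebo 88/125 has 6 + 37 = 43 events, enough for both site and symptom count, yet goes to Fisher.

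**Sparse data it misses.** TQ 118/125 versus placebo 125/125 has 7 + 0 = 7 events. It stays on logistic regression, where the Wald test fails because one arm has no events; Fisher gives p = 0.014. At true TQ 93% and placebo 99%, 24% of trials have fewer than 10 events and no switch.

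**Mirror images.** TQ 119 versus placebo 110 has 6 + 15 = 21 events and goes to Fisher, p = 0.066. With the arms swapped, the same 21 events go to logistic regression. Unadjusted, ln OR = ln(119/6) − ln(110/15) = 0.995, SE = √(1/119 + 1/6 + 1/110 + 1/15) = 0.501, z = 1.99 and p = 0.047. At 21 events the plan would add site, so 0.047 illustrates the different branch and is not the p-value the plan would report.

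**Power.** Exact enumeration, unadjusted Wald on the logistic branch. The pooled rule uses Fisher if combined events are fewer than 10 or an arm has none.

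| TQ / placebo | Always Wald | Plan | Pooled rule |
|---|---|---|---|
| 85 / 70 | 81.7% | 81.7% | 81.7% |
| 95 / 85 | 75.9% | 73.7% | 76.1% |
| 95 / 88 | 49.8% | 44.8% | 49.9% |
| 96 / 88 | 63.9% | 58.3% | 64.5% |
| 97 / 90 | 58.1% | 52.1% | 60.3% |
| 99 / 93 | 38.0% | 58.9% | 63.0% |

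With the arms reversed, the plan declares 96 versus 88 in 63.9% of trials and 99 versus 93 in 40.8%. The pooled rule gives 64.5% and 63.0% either way. Maximum type I error over common rates of 60% to 99.5% is 5.04% under both rules.

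**With site in the model.** A simulation of 4,000 runs (assumed: uneven sites, blocks of 4, site SD 0.5 on the logit scale, unstratified exact fallback) with 5, 10 and 20 sites gives, at 96 / 88, plan 59.9%, 61.2%, 63.0% and pooled rule 62.8%, 64.1%, 65.5%. The gaps are 2.9, 2.9 and 2.5 points. At 99 / 93 they are 1.7, 1.4 and 0.8.

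**Secondary endpoints.** If the rule is read as 95% of TQ patients free of the event, the switch probability is 37% at 94% event-free, 57% at 95%, 77% at 96% and 99% at 98%. Taking hospitalisation rates of 2% and 6% (assumed; the documents give none), TQ 2% versus placebo 6% goes to Fisher in 99% of trials and the reverse in 37%, although both have 125×0.02 + 125×0.06 = 10 expected events.

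**The case against.** The strongest reply is that the switch is a pre-specified contingency that hardly ever operates. The planning basis is "Assuming an 85% clinical recovery rate in the TQ group and a 70% clinical recovery rate in the placebo group", under which it fires in 3 trials in 10,000 and leaves power unchanged. Fisher's test is conservative, section 12 describes methods only in general terms, and a full SAP is to follow before unblinding. All of this stands and limits the size of the point. It does not make the trigger match its stated reason.

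A reader might infer more than the documents support:

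- *That the rule inflates false positives or favours TQ.* It does neither consistently. Type I error is not raised. Against unadjusted Wald, the rule lowers TQ-favouring power at about 93% to 97% recovery and raises it near 99%. Against a likelihood-ratio test it lowers power at 99 / 93 too (78.6% to 58.9%), though that test itself exceeds 5% at high rates (about 6% at 95 / 95). The plan does not name the statistic.
- *That the switch generally discards site adjustment.* Below 20 events the logistic model would omit site as well. When the switch fires, that is 55% of trials at 96 / 88 and 99.8% at 99 / 93.
- *That the 6-point loss is the plan's true loss.* That figure leaves out the site term; with it, the gap is about half.
- *That trials with 10 to 19 events and no switch are missed.* By the ladder's implied limit of 10 for treatment alone, they are not.
- *That the recovery rate picks the test for hospitalisation.* The natural reading of section 12.3.2 applies the rule to each endpoint's own outcome. The asymmetry remains on that reading. Hospitalisation may well be rare, since section 7.2 excludes patients with symptoms "suggestive of possible requirement to hospitalize within 48 hours of enrollment".

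**Conclusion.** The point holds. The trigger does not measure what it is said to measure, and its effect depends on the direction of the result. This should be corrected, but it does not threaten the trial: there is no effect at the planned rates, no inflation of type I error, and a loss of a few points of power from about 92% TQ recovery upward. The unadjusted results assume exactly 125 per arm and a Wald test. The site-adjusted results rest on an assumed site structure, because the number of sites is not stated. The direction of the effect at very high recovery depends on the unnamed test statistic. The inconsistency within section 12.3.1 rests on none of these assumptions.

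**What to change.** In section 12.3.1, delete the 95% TQ-arm trigger and define events as non-recoveries in both arms combined. Keep logistic regression with the existing covariate steps, and name its test statistic. Use an exact test, stratified by site where feasible, only if combined events are fewer than 10 or either arm has none. In section 12.3.2, state the event for each dichotomous secondary endpoint, including "Hospitalization rates due to COVID-19 symptoms (excluding admittance only for administrative or observations purposes", and apply the same trigger to that event. Align the synopsis and the SAP.

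The cost is wording, with no extra patients. Section 12 allows such a change to be documented in the SAP before database lock and unblinding without a protocol amendment. In the cases enumerated, unadjusted power is never below the plan's and is the same whichever arm is better. One drawback is that sites where all outcomes are alike add nothing to a stratified exact test. Replacing the primary test with a Cochran-Mantel-Haenszel test or logistic regression conditional on site is optional and not needed here; it would drop the planned symptom-count covariate from the primary test.
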